The largest fibroid is defined as the fibroid which is the largest at baseline (measured by ultrasound). The fibroid identified at baseline as the largest will be followed up at each scheduled visit.

Fibroids volume measured by ultrasound (mL) $(2) \frac{\pi \times a \times b \times c}{6}$;

a = Largest diameter of the fibroid (cm), b = First diameter perpendicular to largest diameter (cm), c = Second diameter perpendicular to largest diameter (cm)

If only 2 diameters are available, the formula will be the same but the third diameter will be replaced by the mean of the available two diameters.

If only 1 diameter is available, the formula will be: $= \frac{4 \times \pi \times r^3}{3}$; $r = \frac{\text{available diameter of the fibroid (cm)}}{2}$

If one or two diameters are recorded as 0 cm, then those diameters will be considered missing and the rules above will apply.

Volume of 3 largest fibroids measured by ultrasound (mL)

Defined by the sum of the 3 largest fibroid volumes. If less than 3 fibroids are present, the volume of the actual number of fibroids will be summed. The 3 fibroids identified at baseline as the largest will be followed up at each scheduled visit.

Uterine volume measured by ultrasound (mL) $= \frac{\pi \times a \times b \times c}{6}$;

a = Maximum width anteroposterior of uterus (cm), b = Maximum width transverse (cm) of uterus, c = Corpus + cervix length (cm).

If only 1 or 2 diameters are available, the calculation will follow the same rules defined for fibroids volume measured by ultrasound.

Volume of the largest cyst (mL) $= \frac{\pi \times a \times b \times c}{6}$;

a = largest diameter of largest cyst (cm), b = diameter perpendicular to the largest cyst (cm), $c = \frac{a+b}{2}$ (cm)

If only 1 diameter is available, the calculation will follow the same rules defined for fibroids volume measured by ultrasound. If one diameter is recorded as 0 cm, then the value of the diameter will be considered missing and the rule above will apply.

BMD measurements

BMD is assessed using dual-energy X-ray absorptiometry (DEXA). To increase accuracy of the assessment, 2 measurements per location was to be performed at each time point and the mean value will be used for evaluation. If only one scan was performed per location and time point, or one of the two scans is not evaluable, the available valid value will be used as the mean value. Phantom image acquisition is standardized across DEXA imaging facilities according to the instructions specified in an imaging manual. The mean value and percentage change in BMD of each location (the central reading results) from baseline at each time point used for statistical analysis will be calculated by ICON's Medical Imaging group and transferred to Bayer according to the Independent Review Charter.

For BMD baseline, in general, if no Visit 2-repeat scan exists, Visit 2 scan will be used as baseline. Otherwise, Visit 2 -repeat scan will be used as baseline. The BMD baseline visit will be marked in the dataset transferred from ICON's Medical Imaging group.

Repeated measurements at the same visit

If more than one post-randomization measurement is available for a given visit, the first observation will be used in the data summaries if no special reason for the additional observation was provided by the investigator in the CRF, and all observations will be presented in the data listings.

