With the implementation of protocol amendment 9 (Version 6.0), no further subjects were recruited. Subjects that started to a regimen with 3-months treatment courses should finish the treatment course as planned. Subjects that started to a regimen with treatment courses of 6 months duration should finish the first 3 months, if they are currently in the first 84 days of that treatment course, finish the second 3 months, if they are currently beyond day 84 of the treatment course. Thus, with the implementation of protocol amendment 9 and the originally foreseen study design outlined in [Figure 3-1](#) is not applicable anymore for vilaprisan groups. Subjects in treatment group B can continue the study course following the current valid version of the protocol.

With the implementation of Protocol Amendment 10 (version 7.0), this study design as outlined in [Figure 3-1](#) is no longer valid. No subjects will receive further study drug treatment. All subjects who were randomized and started treatment before the temporary pause were asked to have a comprehensive safety evaluation (with particular focus on endometrial, adrenal and skin safety) performed. This also applies to subjects who have completed or discontinued the study before or during the temporary pause, provided they have taken at least one dose of study medication.

Likewise, subjects randomized to treatment group B who are still in the study will be asked to undergo these procedures.

At the time study treatment was terminated, no subjects in subgroup 2 had reached the second year of treatment. Therefore, the statistical analysis will include patients from both subgroups without any distinction.

Figure 3-1 Design overview

Subgroup 1 (about 1 year of treatment)

A1	SCR up to 90 days	RND	12 wk trt	B	12 wk trt	B	12 wk trt	B	12 wk trt	24 wk FUP
A2	SCR up to 90 days	RND	24 wk trt		B	B	24 wk trt		24 wk FUP	
A3	SCR up to 90 days	RND	12 wk trt	B	B	12 wk trt	B	B	12 wk trt	24 wk FUP
B	SCR up to 90 days	RND	Symptomatic nonhormonal medical treatment as determined by the investigators and/or watch and wait						24 wk FUP	

Subgroup 2 (about 2 years of treatment)

A1	SCR up to 90 days	RND	12 wk trt	B	12 wk trt	B	12 wk trt	B	12 wk trt	B	12 wk trt	B	12 wk trt	B	12 wk trt	B	12 wk trt	12 wk FUP
A2	SCR up to 90 days	RND	24 wk trt		B	B	24 wk trt		B	B	24 wk trt		B	B	24 wk trt		12 wk FUP	
A3	SCR up to 90 days	RND	12 wk trt	B	B	12 wk trt	B	B	12 wk trt	B	B	12 wk trt	B	B	12 wk trt	B	B	12 wk FUP

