4.5 Data Rules

Reference Start/End dates

For vilaprisan (VPR), the reference start and end dates refer to the first and last study drug intake and will be identified based on the eCRF entry (EXCATN=1). For subjects with study drug exposure unknown, the randomization date will be used as the reference start date, and the end date of last scheduled/ unscheduled visit according SV (Subject Visits dataset) will be used as the reference end date.

Missing or partially missing eCRF end dates will be replaced by the date of the last study drug intake according to the diary. In case there is no study drug intake recorded in the diary, the date of the last available visit/contact will be used, which is the maximum of the end date of last scheduled/ unscheduled visit according SV (Subject Visits dataset), and the “last visit” as collected on the eCRF page for Disposition dataset. For subjects randomized to VPR who did not take any treatment (FAS not SAF), the last available visit date will be used as the reference start date and the reference end date.

For treatment group B the reference start date is defined by the randomization date. The reference end date is defined by the start date of the End of Treatment (EoT) visit (unscheduled EoT visits not considered). Missing EoT visit dates will be replaced by the end date of the last available visit before the safety closeout visit (refer to Table 4-1). If a subject in treatment group B has no safety

closeout visit, missing EoT visit dates will be replaced by the date of last scheduled/ unscheduled visit according SV (Subject Visits dataset).

For both VPR and treatment group B, the reference end date after the missing replacement with the rules defined above should be no earlier than the reference start date. Otherwise, the reference end date will finally be replaced by the reference start date.

For any analysis, if date of first study drug exposure/ date of last study drug exposure is used, the reference start/end date for treatment group B defined as above will be used for the analysis in treatment group B, if applicable.

Table 4-1 Replacement rules for missing reference start/end dates and TP start/end dates

	Choice	VPR regimens	Treatment group B
Reference start date	1 st	eCRF	Randomization date
	2 nd	a. If study drug exposure unknown, use randomization date b. If no study drug exposure (FAS not SAF) use SV last visit end date	
Reference end date / Last TP end date	1 st	eCRF	EoT visit start date

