	2 nd	Diary	Last visit before the safety closeout visit
	3 rd	Max (SV last visit end date, “last visit” from eCRF)	SV last visit end date
	4 th	If no study drug exposure (FAS not SAF) use SV last visit end date	
		Reference end date will finally be replaced by maximum of reference start date and reference end date.	
TP start date	1 st	eCRF (TP1: reference start date) Exception 6/2 regimen: split protocol planned TPs with 168 days, assign start and end dates of these with CRF collected for planned TPs and derived start and end dates of split TPs.	TP1: reference start date TPs will be defined as consecutive 84-day time intervals starting with the date of randomization.
TP end date (excluding last TP)	1 st	eCRF exception 6/2 as above	
TP end date (last TP)	1 st	Reference end date	

eCRF = electronic case report form; EoT = end of treatment; SV=subject visit; TP = treatment period; VPR = vilaprisan

Treatment period

For subjects in treatment groups A1, A2, and A3, each treatment period (TP) consists of three subsequent 28-day periods. In case of premature discontinuation of study drug the last 28-day period of the respective treatment period might be shorter than 28 days. If a subject took the study drug for more than 84 days of a treatment period, the respective treatment period will be longer than 84 days, in contrast. Subjects treated in 3/1 and 3/2 regimens, have the first break after TP 1. Subjects treated in 6/2 regimens have two planned TPs before the first break.

The definition of TP here described which will be used in the analysis, differs from the definition of TP used in the protocol and Section 3 to describe the 6/2 treatment regimen. The definition used in the analysis allows for a better comparison between treatment regimens and is consistent with the reporting of other studies of the VPR project.

The first TP starts with the reference start date, the last TP ends with the reference end date. Start and end of a TP will be identified based on eCRF entries (EXCATN=1).

In 6/2 regimen, the protocol plans for TPs with 168 days each. The CRF only collects start and end dates of these protocol planned TPs.

For the analysis, the planned protocol TPs are split into 2 Analysis TPs:

- The first Analysis TP is assigned first available odd TP number and ends with day 84 (or the maximum number of available days if less than 84 days are reported).

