6.5.1 Primary safety variable

The primary safety variable is the percentage change in BMD of lumbar spine (using the central reading results) from baseline to about one year after SoT. One year is defined as ‘Month 12 on treatment’ in Table 6-1, i.e. Day 300 after reference start date to Day 420 after reference start date, but no later than the reference end date + 60 days.

The primary safety variable will be analyzed using descriptive statistical methods and two-sided 95% confidence interval (CI) for the mean difference for the percentage change in BMD of lumbar spine from baseline to about one year after SoT will be calculated for each vilaprisan treatment group as compared to treatment group B. Additionally, two-sided 95% CI for each treatment group will be calculated. The primary variable is assumed to be at least approximately normally distributed.

For the percentage change in BMD of lumbar spine from baseline to other time points defined in Table 6-1, the descriptive statistics will also be provided by treatment group.

The percentage change in BMD of lumbar spine from EoT BMD will also be evaluated using summary statistics by treatment group and time interval or month for post treatment period defined in Table 6-1.

The time intervals and month named in Table 6-1 will be presented in tables and figures unless otherwise specified. Month equals 30 days.

Table 6-1: Definition of month and time intervals for BMD summary

	Month	Time interval
Baseline	Baseline	Baseline if no Visit 2-repeat scan exists, Visit 2 scan will be used as baseline. Otherwise, Visit 2 -repeat scan will be used. The BMD baseline visit will be marked in the dataset transferred from ICON’s Medical Imaging group. (refer to section 4.5)
On treatment period : From reference start date to reference end date + 60 days	Month 1	N/A
	Month 2	If a BMD value performed after the reference start date has been marked as baseline value, it will be analyzed as baseline value and will be excluded from the analysis for on treatment period.
	Month 3	
	Month 4	
	Month 5	Month 6 on treatment Day 120 after reference start date to Day 240 after the reference start date, but no later than the reference end date + 60 days
	Month 6	
	Month 7	
	Month 8	
	Month 9	N/A
	Month 10	Month 12 on treatment Day 300 after reference start date to Day 420 after reference start date, but no later than the reference end date + 60 days
	Month 11	
	Month 12	
	Month 13	
	Month 14	

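### When a vilaprisan end date is in neither the eCRF nor the diary, the off-drug safety closeout visit can become the end of treatment, while group B's rule excludes that visit

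*SAP*

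**What the plan says.** Section 4.5 (Reference Start/End dates) and Table 4-1 give each arm an order of sources for the reference end date.

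- **Vilaprisan:** the eCRF date of last intake comes first. The diary comes second: "Missing or partially missing eCRF end dates will be replaced by the date of the last study drug intake according to the diary". The third choice is "In case there is no study drug intake recorded in the diary, the date of the last available visit/contact will be used", defined as the later of the last date in the visit dataset and the last visit on the disposition page. A separate sentence gives subjects with unknown exposure their last visit in the visit dataset.
- **Group B:** the EoT visit comes first. Then: "Missing EoT visit dates will be replaced by the end date of the last available visit before the safety closeout visit". Only a subject with no closeout visit gets the last visit of any kind.

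Section 3 places the closeout visit under Amendment 10, when "No subjects will receive further study drug treatment". It extends closeout to women who had already completed or discontinued, if they took at least one dose. Vilaprisan subjects are asked for a BMD scan at least 6 months after last intake.

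Section 6.5.1 and Table 6-1 build the BMD windows on the reference end date. The on-treatment period runs to that date plus 60 days. The primary Month 12 window is Day 300 to 420, "but no later than the reference end date + 60 days". EoT BMD is the reference end date ± 60 days, and EoFUP BMD may not be earlier than that date plus 60 days.

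**The concern.** The closeout exclusion in group B's rule recognises that closeout is not a sensible marker for the end of treatment. The vilaprisan fallback lacks that bound, although closeout may come many months after the last tablet.

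The reference end date fixes the end of the last treatment period, the treatment and follow-up phases, the BMD windows and, through last exposure, the AE windows. If it lands on closeout, data collected off drug are relabelled as on treatment. For BMD this touches the primary safety variable and the recovery analysis of Table 6-2. The exposure tables would not reveal it, because section 6.1.8.1 computes treatment duration without replacing missing dates.

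**Working it through.** The SAP states no figure on this point, so there is nothing to reproduce. I applied the Table 4-1 order and the Table 6-1 windows to invented subjects. The windows come from the SAP. The subject days are assumptions, counted from the reference start date.

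**1. General result.** Let L be the true last dose, S the scan day and R the reference end date used. A scan is on treatment if S ≤ R + 60. A recovery scan has S ≥ L + 180 (6 months of 30 days).

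- With R = L, the cap is L + 60, so such a scan is never on treatment.
- With R = last visit and the scan on or before that visit, S ≤ R, so it is always on treatment.
- It falls in the Month 12 window when 300 ≤ S ≤ 420, which requires L ≤ 420 − 180 = 240.

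**2. Illustrations.** In each row the dates ahead of the fallback are missing.

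| Assumed subject | R as written | Scan(s) as written | With the true end date |
|---|---|---|---|
| Vilaprisan: last dose 168, scan and closeout 348 | 348 (cap 408; EoT window 288–408) | Month 12 on treatment and EoT BMD | Cap 228; 180 days post-treatment, can be EoFUP |
| Vilaprisan: last dose 168, scan 348, closeout 560 | 560 (cap 620; EoT window 500–620) | Month 12 on treatment | Post-treatment, can be EoFUP |
| Vilaprisan: last dose 340, scan and closeout 520 | 520 (cap 580; EoT window 460–580) | On treatment after Month 14, and EoT BMD | Cap 400; post-treatment |
| Group B: EoT 336, follow-up visit 504, closeout 540, scans at both | 504 (cap 564) | Both on treatment | Cap 396; both post-treatment |
| Group B: as above, closeout 700 | 504 (cap 564) | Day 504 on treatment; Day 700 post-treatment | Both post-treatment |

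The last two rows show that group B can also be misdated, but through a follow-up visit (336 + 24 × 7 = 504). Closeout itself is never its end date if the subject attended closeout.

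**3. Follow-up phase.** Section 4.5 starts follow-up the day after treatment ends and closes it on the later of the last visit date and the eCRF last visit. That closing date is essentially the vilaprisan third-choice end date. Follow-up then starts on R + 1 and ends on R, so the subject has essentially none. An EoFUP scan would have to fall at or beyond R + 60, after the last recorded visit.

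**4. Reach into the primary window.** Assume no closeout before the Amendment 10 date (21 Nov 2019) and no treatment start after the Amendment 9 date (11 Dec 2018), which are 345 days apart. A closeout-day scan falls on Day 420 or earlier only for starts from 21 Nov 2019 − 420 days = 27 Sep 2018 onward. That leaves 27 Sep to 11 Dec 2018, or 420 − 345 = 75 days. For earlier starters a closeout-day scan falls after Month 14, though an earlier follow-up scan can still be drawn into Month 12.

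**The case against.** **The trigger is narrow.** The eCRF date must be missing or partial and the diary must hold no intake, or exposure must be unknown. The subject must also have attended closeout. This stands: the SAP gives no count, and it could be zero.

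**Group B is affected too.** A reader might infer that only vilaprisan data can be mislabelled. The documents do not support that, as the last two rows of the table show. The asymmetry concerns the closeout visit itself.

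**The exposure-unknown case is weak.** The closeout evaluation and the SAF both require at least one dose, so such a subject may not reach the BMD or AE tables. This stands, but leaving that rule unbounded would be inconsistent.

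**AEs already have a conservative default.** Section 6.5.3.5 treats an AE as treatment-emergent unless there is clear evidence otherwise. When the last dose is unknown, counting late AEs follows that default. This largely stands for AEs. It does not apply to BMD windows.

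**The recovery scan need not enter the EoT window.** It is requested, and for vilaprisan section 3 does not tie it to the closeout visit. It could fall in the window, but one cannot say it would.

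**There are partial safeguards.** Section 5.1 repeats the BMD analyses on the modified SAF, whose exclusion criteria sit in a separate document. That may remove such subjects there, but it leaves the SAF analysis unchanged.

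**Conclusion.** The point holds in limited form. As written, the vilaprisan rules can set the end of treatment at an off-drug visit that group B's rule excludes. For any subject so affected, off-drug BMD can enter the on-treatment, Month 12 or EoT windows, and the EoFUP comparison can be lost.

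The size cannot be derived. It depends on how many subjects have no usable eCRF or diary end date and attended closeout. The 345 days between the two amendments might be read as the dating error. It is not: neither date is a last dose or a closeout visit, and Amendment 9 let ongoing courses run on. The firmer figure is that a recovery scan timed as requested is at least 6 months off drug, three times the 60-day cap (180 / 60).

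Nor is the net direction fixed. If bone recovers off drug, a recovery scan placed in Month 12 makes vilaprisan loss look smaller. The worst-outcome table in section 6.5.1 takes the worst value over the treatment period, so lengthening that period can only leave the result unchanged or worsen it.

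This is worth correcting because the remedy is already in the SAP, not because a material effect on the results has been shown.

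**What to change.** In section 4.5 and Table 4-1, replace the vilaprisan third choice. When the eCRF and diary end dates are both missing, use the EoT visit date. If that is missing, use the last visit before the safety closeout visit. Apply the same bound to subjects with unknown exposure. Report how many subjects in each arm have a replaced reference end date and from which source.

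The cost is one line of text and one table row, plus the matching derivation code. There are two limits:

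- The last visit before closeout may still be a follow-up visit, so the change narrows the error without removing it, as in group B.
- Some AEs of uncertain timing would move from treatment-emergent to post-treatment. If the conservative default of section 6.5.3.5 is preferred, apply the bound to the BMD and treatment-phase windows only, and say so.

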In general, the last valid, non-missing value prior to the Reference start date will be considered as baseline value. For variables analyzed by 28-day periods, the baseline period corresponds to the last 28 days before the reference start date. This definition does not apply to analyses related to menstrual blood loss where a specific definition for baseline menstrual blood is defined (see baseline menstrual blood loss for 28 days).

Bleeding caused by conducting endometrial biopsy

If an endometrial biopsy was conducted, bleeding on the day of intervention and the 3 days thereafter will not be considered in the bleeding related evaluation, i.e., bleeding/spotting on the day of biopsy and 3 days thereafter will not be considered as day(s) with bleeding/spotting and MP values will be set to 0 mL. This rule is applicable for all bleeding related efficacy analyses.

A biopsy will be regarded as conducted if the intervention was attempted, either successfully or unsuccessfully. Successful means that the date of biopsy is given and 'Biopsy sample obtained - Not done' is not ticked in the eCRF. Unsuccessful means that the date of biopsy is given, 'Biopsy sample obtained - Not done' is ticked in the eCRF, and the reason 'Unsuccessful attempt' is selected.

Baseline menstrual blood loss for 28 days

Baseline menstrual blood loss for 28 days is defined as the sum of volume of menstrual blood loss data of respective days in the baseline cycle. If baseline cycle length is more than 28 days, only data from the first day of cycle to the 28th day of cycle will be used. If baseline cycle length is less or equal than 28 days, data from the first day of cycle to the last day of cycle will be used.

Baseline menstrual cycle

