The left margin may be displaced backwards at maximum up to the end of the first bleeding episode when treatment was started in respective treatment period. For TP with an even number in the 6/2 regiment, the left margin may be displaced backwards at maximum up to the end of the first bleeding episode of the preceding odd-numbered TP from the same protocol defined 168-day TP when treatment was started.

Absence of bleeding (spotting allowed) during the last 28 days of the treatment; based on the UF-DBD

Absence of bleeding is defined as no bleeding (spotting allowed) during the last 28 days of the respective treatment period based on the UF-DBD. For missing data replacement please refer to section 4.3.

The last days under treatment with 28 days with non-missing bleeding eDiary data will be used to calculate whether absence of bleeding occurred. Thus, if the last 28 days of treatment include days with missing bleeding eDiary data, the left margin of this interval will be displaced backwards in time and step-wise until the required number of 28 non-missing values are included.

The left margin may be displaced backwards at maximum up to the end of the first bleeding episode when treatment was started in respective treatment period. For TP with an even number in the 6/2 regimen, the left margin may be displaced backwards at maximum up to the end of the first bleeding episode of the preceding odd-numbered TP from the same protocol defined 168-day TP when treatment was started.

Subjects who discontinue treatment prior to completion of 8 weeks of treatment in the respective TP will be considered as not experiencing absence of bleeding.

Number of bleeding days

Number of bleeding days is defined as number of bleeding days (based on the UF-DBD) from Day 1 of the first treatment period until one day before the theoretical next treatment period would start after the last study treatment period. Definition of the day before theoretical next treatment period end date, i.e., theoretical end date for the break period, refers to the rules defined in break period above.

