All information available at the time of analysis will be included. For example, for a subject allocated to treatment group A1 (3/1 regimen) in subgroup 1 who completed the full planned treatment, the number of bleeding days will be counted from the 1st day of TP1 until the date when a new TP would theoretically start following the end of TP4 and the required bleeding episode that follows TP4, without gaps. If a subject withdrew while receiving treatment in TP3, the number of bleeding days will be considered from the 1st day of TP1 until the date when a new TP would theoretically start following the end of TP3 and the required bleeding episode that follows TP3, irrespective of the length of the incomplete TP3.

For subjects who did not start the next planned TP, due to the study being temporarily paused or any other reasons, as described in the section 'Break period', a theoretical end of break period will be derived in these cases. The number of bleeding days will be counted until the derived end of break period.

The period for evaluation of "number of bleeding days" for the treatment group B starts on the reference start date and ends on the reference end date. A theoretical end of break period following the reference end date will not be generated.

The analysis of the number of bleeding days from these pre-determined evaluation periods will be normalized to 28 days and 365 days.

Onset of amenorrhea for analysing time-to-event data

Onset of amenorrhea is defined by the first day for which the menstrual blood loss (assessed by MP) for all subsequent 28-day periods up to the end of the treatment period is <2 mL. Amenorrhea status will be assessed for each of the subsequent, overlapping 28-day periods within a treatment period. The censoring mechanism is assumed to be non-informative and the subjects will be handled as right-censored, if applicable. If a subject completed the 84 days of a treatment period and did not experience an onset of amenorrhea, the subject will be censored on Day 57 of the treatment period.

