5.1 Assignment of analysis sets

Final decisions regarding the assignment of subjects to analysis sets will be made during the review of study data and documented in the final list of important deviations, validity findings and assignment to analysis set(s) (see Section 4.6).

Full analysis set (FAS): All subjects randomized to vilaprisan treatment groups, excluding randomized subjects who did not start TP 1 due to the study being temporarily paused and all subjects randomized to treatment group B will be included in the FAS. Subjects will be analyzed as randomized.

Safety analysis set (SAF): All subjects randomized to vilaprisan treatment groups who took at least 1 dose of study drug. will be included in the SAF. Subjects will be analyzed as treated.

All subjects randomized to treatment group B will be included in the SAF. Subjects will be analyzed as treated, regardless whether they actually took any medication (i.e., symptomatic, nonhormonal medical treatment).

Modified SAF: will include all subjects in the SAF without any validity findings which are those that may potentially affect the primary safety endpoint. Validity findings leading to exclusion from the modified SAF will be specified in the 'Specification of assessment criteria and identification requirements', which will be finalized before database lock. Subjects will be analyzed as treated.

All safety analyses will be performed on the SAF population. The FAS will be used for the display of all other variables. The analysis for the primary safety endpoint and all BMD related endpoints will be performed on the Modified SAF as well.

Screened subjects who are not included in the FAS will be used solely in disposition tables and will be listed only in Section 16 of the clinical study report, as described elsewhere.

6. Statistical Methodology

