6.2.2 Secondary efficacy variable

The analyses for all the secondary efficacy variables will be conducted in the FAS population.

The secondary efficacy variable is number of bleeding days, as defined in Section 4.5.

Number of bleeding days will be shown by treatment groups for the treatment phase only plus 1 or 2 bleeding periods following the end of the last TP depending on treatment regimen.

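### Randomised but untreated vilaprisan subjects in the FAS get a one-day treatment phase at their last visit, so their normalised bleeding-day value carries almost no information

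*SAP*

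**What the plan says.** SAP section 4.5 (Reference Start/End dates) covers vilaprisan subjects who took no study drug: "the last available visit date will be used as the reference start date and the reference end date". Table 4-1 repeats this: "If no study drug exposure (FAS not SAF) use SV last visit end date". In the same section, group B and vilaprisan subjects with unknown exposure start at the randomisation date.

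Section 5.1 removes from the FAS only untreated vilaprisan subjects of one kind, "excluding randomized subjects who did not start TP 1 due to the study being temporarily paused". Those untreated for any other reason remain, analysed as randomised. Section 6.2.2 then states: "The analyses for all the secondary efficacy variables will be conducted in the FAS population". The variable is number of bleeding days.

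Three further rules in section 4.5 carry the reference dates into that variable:
- Treatment periods: "The first TP starts with the reference start date, the last TP ends with the reference end date".
- The vilaprisan bleeding-days period runs "from Day 1 of the first treatment period until one day before the theoretical next treatment period would start". If no bleeding episode follows, the break lasts until observation ends.
- The counts "will be normalized to 28 days and 365 days".

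For baseline, the general rule is that "the last valid, non-missing value prior to the Reference start date will be considered as baseline value". The baseline phase ends on the day before the reference start.

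**The concern.** Time zero for an untreated subject is placed at the end of her observation instead of at its beginning. What the plan treats as her treatment phase is one calendar day, and a count over one day is scaled to a year. The result is either a zero or an extreme value, and neither reflects how she bled after randomisation. Her actual post-randomisation diary days lie before the reference start and do not enter the variable.

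The label in Table 4-1 (in the FAS but not the SAF) shows that the plan expects such subjects. Amenorrhea and absence of bleeding each have an 8-week rule for short treatment; number of bleeding days has no counterpart. At stake are the mean, SD and maximum of the secondary efficacy variable in the vilaprisan groups, and the smaller section 7 subgroups, which use the same variable.

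**Working it through.** The SAP gives no figure on this point, so there is none to reproduce. What follows applies its own rules.

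**Step 1, treatment period.** Start and end are both the last visit, so the length is end - start + 1 = 1 day. Table 4-1 sets the TP1 start to the reference start date and the last TP end to the reference end date, so TP1 is that day.

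**Step 2, bleeding-days period.** Let g be the days of observation after that visit, with no later bleeding episode starting. Under the break rule the period is L = 1 + g. If the visit is the end of observation, g = 0 and L = 1.

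**Step 3, normalisation.** With b bleeding days, the value is b/L x 28 or b/L x 365. The contribution of each bleeding day is:

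| g | L | per 28 days | per 365 days |
|---|---|---|---|
| 0 | 1 | 28 | 365 |
| 1 | 2 | 14 | 182.5 |
| 7 | 8 | 3.5 | 45.6 |
| 30 | 31 | 0.9 | 11.8 |

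At g = 0 the only possible values are 0 (b = 0), or 28 and 365 (b = 1). Two rules modify this. Without a diary entry that day the value may be missing. If a biopsy was attempted on that day or in the 3 days before, the biopsy rule in section 4.5 makes the day non-bleeding and the value is 0.

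**Step 4, effect on a group mean.** If the other subjects have mean m and the group has n subjects in all, one subject scoring 365 shifts the mean by (365 - m)/n. Assume m = 30 (not in the SAP):
- n = 50: 335/50 = 6.7 days
- n = 100: 335/100 = 3.35 days
- n = 150: 335/150 = 2.2 days

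One subject scoring 0 shifts it by -30/n, or -0.3 at n = 100.

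The spread moves more. With an assumed SD of 20 and two of 100 subjects scoring 365, the mean is (98 x 30 + 2 x 365)/100 = 36.7. The SD is the square root of [(98 x (20² + 30²) + 2 x 365²)/100 - 36.7²], which is 50.9.

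**Step 5, comparison with a value from randomisation.** Assume 5 to 7 bleeding days per 28 days in an untreated subject (not in the SAP). Counted from randomisation she would score 5 x 365/28 = 65 to 7 x 365/28 = 91 per 365 days. Against that, a value of 365 is too high by 274 to 300 and a value of 0 is too low by 65 to 91. At n = 100 the group mean is off by +2.7 to +3.0 or by -0.65 to -0.91.

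**Step 6, baseline.** The baseline phase ends the day before the last visit, so everything between randomisation and that day falls inside it. Where the general rule applies, the baseline value can be a post-randomisation one. Section 6.2.3.3 ties the largest-fibroid baseline to randomisation, and menstrual blood loss has its own baseline cycle in section 4.5, so these two are not governed by the general rule.

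**The case against.** The strongest reply is that the consequence may be negligible. Subjects untreated because of the pause are already out of the FAS. The rest are not counted anywhere in the SAP, and there may be few or none. The variable is summarised descriptively with no test, and the median is reported beside the mean. The primary BMD variable and the other safety analyses use the SAF or modified SAF, which contain no untreated vilaprisan subjects. All of this stands and limits the weight of the point.

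A reader might also infer four stronger things that the document does not support:
- That every such subject scores exactly 0 or 365. The break rule lengthens the period if observation continues past the visit, and the diary and biopsy rules can make the value missing or 0. Table 4-1 adds ambiguity: read in order, its third choice for the end date (the later of two last-visit dates) comes before the entry for untreated subjects.
- That all follow-up data become baseline values. Only the last value before the reference start does so, data from the visit day itself fall in the treatment phase, and two baselines have their own definitions.
- That one subject scoring 365 adds 365/n to the mean. That is her gross share; the shift is (365 - m)/n.
- That any difference in time zero is an error. Treated vilaprisan subjects start at first intake and group B at randomisation by design. The unexplained contrast is with vilaprisan subjects of unknown exposure, who start at randomisation.

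None of this gives the one-day period a meaning, and the SAP does not say that these subjects are left out of the bleeding-days summary.

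**Conclusion.** The point holds in a limited form. Sections 4.5, 5.1 and 6.2.2 together send randomised but untreated vilaprisan subjects into the bleeding-days analysis with a period of one day, or slightly longer if observation continues. No minimum length applies before scaling. The typical result is 0, or 28 and 365; with 7 further days of observation each bleeding day still counts as about 46 per 365 days. Each subject at 365 shifts a group mean by about 2.2 to 6.7 days for n = 150 down to 50, assuming a mean of 30 in the others. Group sizes, that mean and the number of subjects affected are not in the SAP. The general baseline for these subjects can also be a post-randomisation value. The damage is confined to descriptive FAS efficacy summaries, but the rule produces a value without meaning and the correction is cheap.

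**What to change.** In section 4.5 and Table 4-1, use the randomisation date as reference start for untreated vilaprisan subjects in the FAS, and keep the last available visit as reference end. In Table 4-1, put the untreated-subject entry ahead of the third choice for the end date so that text and table agree.

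Under Number of bleeding days, add one sentence: for these subjects the period runs from reference start to reference end and no theoretical break is generated, as for group B. Changing the table alone would not be enough, because the end of the period is set there and under Break period. The safety closeout visit is not a suitable anchor: section 3 asks for that evaluation only from vilaprisan subjects who took at least one dose.

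The cost is one changed table entry, one sentence of exception and minor reprogramming. The number of such subjects per group should be reported beside the bleeding-days table. If the intention is instead to leave them out of that summary, the SAP should say so.
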